The sample size was estimated assuming a 5% alpha error and 80% study power. The overall success rate after 1 year was 95% for chemo-mechanical caries removal,⁽³¹⁾ whereas it was 67% for traditional caries removal.⁽³²⁾ Based on the difference between independent proportions, the sample size was calculated to be 30 patients per group, increasing to 36 patients to make up for lost follow-up cases. Total sample = number per group x number of groups = 36 x 3 = 108 patients.

Software

The sample size was based on Rosner's method⁽³³⁾ calculated by G*Power 3.1.9.7. ⁽³⁴⁾

Eligibility criteria

The participants enrolled in this study will be selected after fulfilling the following criteria:

Inclusion Criteria

- Healthy children aged 8-10 years old.
- The presence of at least one deep carious class 1 lesion in the first permanent molar with a score of 5 or 6 according to the International Detection and Assessment System (ICDAS), detected by visual-tactile inspection to assess lesion severity. ⁽³⁵⁾ (APPENDIX I, Tables 1)

Exclusion criteria

- Children reporting spontaneous or elicited pain from caries or showing any signs of pulpal infection, swelling or abscess.
- Pulpal exposure or bleeding during the excavation procedure
- Children presenting with special health care needs or undergoing medical treatment for chronic or acute diseases affecting salivary flow.
- Allergy or sensitivity to any of the materials included in the study.

Randomization technique and allocation⁽³⁶⁾

- Subjects complying with the inclusion criteria will be randomly assigned to one of the treatment groups, using a computer-generated list of random numbers to either the Brix 3000, Papacarie duo gel group (www.random.org) or ART approach (Hand excavation).
- Allocation will be performed by a trial independent individual and the allocation ratio is intended to be equal (1:1:1).

Allocation concealment⁽³⁷⁾

An assistant will be responsible for giving each participant a serial number that will be used for his/her allocation. A duplicate of this number will be kept in an opaque envelope indicating to which group the patient belongs. This envelope will be kept by a trial independent individual who will be assigned the role of opening it only at the time of intervention; so that the group to which the child is allocated is concealed from the investigator. Grouping Participants will be randomly and equally allocated to one of the three treatment groups:

Grouping

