- 1- Clinical effectiveness of each material during the follow up period at 3-, 6- and 12-months intervals confirmed with radiographic findings at 6- and 12-month intervals.
- 2- Timing required for complete caries removal following each caries removal method
- 3- Participants' subjective pain reaction following each caries removal method.
- 4- Antimicrobial effect of both CMCR agents by comparing the colony forming units (CFU) at the treatment visit before and after application of each agent compared to conventional caries removal method.

Follow up

All patients will be recalled after 3-, 6- and 12-month intervals. On the day of the recall appointment, patient preparation will be done as mentioned before.

Outcome assessment

- 1- Restorations which will receive a score of 0, 1 or 7 will be considered successful while those having a score of 2, 3, 4 or 8 will be considered failures.
- 2- Any clinical sign and symptoms teeth with pain, intraoral or extra oral abscess formation and fistula formation will be recorded as unsuccessful treatments
- 3- Any periapical lesions on radiography during follow-up will be recorded as unsuccessful treatments.

Study Plan

[figure not shown]

Figure 1: Flow chart of the study plan

STATISTICAL ANALYSIS

The statistical Package for Social Sciences (SPSS)* version 27.0 for Windows will be used for data analysis.

All data will be collected; The Chi square test will be used to compare the difference between the three groups regarding the clinical success, the T-test or the Mann-Whitney U test will be used to analyze the differences between the microbiological samples. The data will be graphically presented with suitable graphs. The level of statistical significance will be set at 5%.

* SPSS Inc., Chicago, IL, USA

ETHICAL CONSIDERATIONS

1. The research protocol will be approved by the Research Ethics Committee of Alexandria University Faculty of Dentistry (IRB No. 001056 –IORG 0008839) prior to any research-related activities.
2. All research activities involving human subjects will abide by the Declaration of Helsinki⁽⁵³⁾ and other ethical guidelines adopted by the Research Ethics Committee of Alexandria University Faculty of Dentistry.
3. Benefits:
 - It will provide caries treatment for young permanent molars in children using minimally invasive atraumatic procedures.
 - It will allow overcoming the disadvantages of conventional treatment with local anesthesia

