 - Support the use of chemo-mechanical caries removal agents as a more convenient substitute conventional method for caries removal.
4. Harms/Risks: Nothing.
5. Privacy and confidentiality:

Each participant will be provided with a serial number that will only be accessible to the principal investigator. No data regarding the identity of the participants will be shared under any circumstances. All participants or their guardians must provide a written informed consent prior to any procedures.

DURATION OF THE STUDY

Estimated time: 17 Months.

Tasks \ Months	1	2	3	4	5	6	7	8	9	10	11	12	13	14	15	16	17
Purchase material	✓																
Patient recruitment		✓	✓														
Treatment procedures			✓	✓													
Evaluations																	
1. Clinical and radiographic success of the CMCR				✓	✓	✓	✓	✓	✓	✓	✓	✓					
2. Time required for caries removal				✓													
3. Subjective pain assessment following each method				✓													
4. Microbiological assessment				✓													
5. OHRQL questionnaire				✓													
Data management and statistical analysis													✓				
Writing thesis														✓	✓	✓	
Thesis submission																	✓

ESTIMATED BUDGET

Estimated total budget: 45,000 LE

No	Materials	Total price (LE)
1	Materials	20000
2	Microbiological assessment	15000
3	Statistical analysis	2000
4	Computer services	2000
5	Printing services	2000
6	Publication cost	3000
7	Others	1000
Total		45000

PROBLEMS ANTICIPATED

The main problems facing the study are:

- 1- The expenses of used materials.
- 2- The recruitment of patients.
- 3- The microbiological assessment procedures.

PUBLICATION POLICY

This study will be sent for either national or international journals for publications.

The order of name will be:

1. [name]
2. [name] [name]
3. [name] [name]
4. Assoc. [name] [name]

REFERENCES

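### The ethics section states that there are no harms, while pulp exposure during the allocated procedure is an exclusion and so would be neither a failure nor a reported harm

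*Combined protocol and SAP*

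**What the plan says.** Ethical Considerations, item 4, reads in full "Harms/Risks: Nothing". Elsewhere the protocol says the following.

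- **Exclusion criteria** list "Pulpal exposure or bleeding during the excavation procedure" and, separately, "Allergy or sensitivity to any of the materials included in the study".
- **Allocation concealment** has an independent person holding the envelope and "opening it only at the time of intervention".
- **Baseline examination and Radiographic evaluation** schedule periapical films before enrolment, directly after treatment, and at 6 and 12 months.
- **Intervention** omits local anesthesia unless it proves necessary.
- **Outcome assessment** lists pain with "intraoral or extra oral abscess formation and fistula formation will be recorded as unsuccessful treatments", and adds: "Any periapical lesions on radiography during follow-up will be recorded as unsuccessful treatments". The same list holds restoration scores 2, 3, 4 and 8 as failures.
- **Clinical evaluation** removes scores 5 and 6 from the analysis. In Appendix IV, code 6 includes an extracted tooth.
- **Statistical Analysis** states: "The Chi square test will be used to compare the difference between the three groups regarding the clinical success".

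The supplied text has no adverse-event definition, no recording procedure and no separate summary of harms by arm.

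**The concern.** A risk section that says there is nothing to report cannot stand beside a protocol that foresees pulp exposure, lists abscess and fistula as possible results, and adds films in children aged 8 to 10. The ethics committee is asked to approve that section.

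The statistical stake is larger than the wording. Pulp exposure is the procedural harm closest to the trial's rationale. The Introduction cites an in vitro comparison of three removal methods to argue that chemo-mechanical removal spares dentin and so helps keep the pulp vital. If children with an exposure are removed through the exclusion list, the trial loses the direct evidence on that argument. The loss may also differ by arm, because the event arises under the assigned method.

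**Working it through.** **1. The plan's own sample size.** Inputs from Sample size estimation: success 95% and 67%, alpha 5%, power 80%. Sidedness is not stated; two-sided is assumed. With mean proportion (0.95 + 0.67)/2 = 0.81:

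n = [1.96 × √(2 × 0.81 × 0.19) + 0.8416 × √(0.95 × 0.05 + 0.67 × 0.33)]² / 0.28² = (1.087 + 0.436)² / 0.0784 ≈ 29.6, so 30 per group.

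This matches the plan. The protocol raises 30 to 36, and 36 × 3 = 108. These figures are not in dispute; 36 is used below as the arm size.

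**2. Films.** One before enrolment, one directly after treatment, two at follow-up: 1 + 1 + 2 = 4 per tooth. With one tooth per child, 4 × 108 = 432.

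**3. Where each event goes.**

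| Event | Counted as failure? | Compared by arm? | Shown separately as a harm? |
|---|---|---|---|
| Pain, abscess or fistula at follow-up | Yes | Yes, within success/failure | No |
| Periapical lesion | Yes | Yes, within success/failure | No |
| Pain of the procedure | No | Yes, a listed outcome (no test named) | As its own outcome |
| Pulp exposure or bleeding in excavation | No, an exclusion | No | No |
| Extracted tooth (code 6) | No, left out of the analysis | No | No |
| New reaction to a material | Not stated | No | No |
| Anesthesia use | Not stated | No | No |

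**4. Timing of pulp exposure.** The assigned method determines how the caries is excavated, so the envelope must be open before excavation starts. An exposure in that procedure therefore follows allocation and cannot act as a screening criterion.

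**5. Effect on the success rate.** Suppose an arm of 36 has e exposures and f later failures, with no other loss. Removing exposures reports (36 − e − f)/(36 − e). Counting them as failures reports (36 − e − f)/36. The first is higher whenever e > 0 and some children succeed, and the gap grows with e. If e differs by arm, the comparison shifts. The documents give no value for e.

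**6. What 36 per arm can show about harms.** Normal approximation, two-sided 5%, with assumed event rates that are not from the protocol:

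| Assumed rates | Power |
|---|---|
| 2% against 10% | about 30% |
| 5% against 15% | about 29% |
| 5% against 20% | about 49% |

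For an arm with no event, the exact one-sided 95% upper limit is 1 − 0.05^(1/36) = 8.0%; with 30 observed it is 9.5%. This holds for any arm of that size and is given only for scale.

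**The case against.** The strongest reply is that the protocol does collect harm-type events. Postoperative pain, signs of pulpitis, percussion and fistula are assessed at 3, 6 and 12 months. Pain, abscess, fistula and periapical lesions count as failures, and clinical success is tested across arms. Procedural pain is a listed outcome, and the one-week questionnaire covers oral symptoms. This stands: a reader might infer that no harm is collected or compared, and the documents do not support that. The reply does not reach pulp exposure, extraction, reactions to materials or anesthesia use. Nor does pooling show whether arms with equal failure counts differ in abscesses, since defects and wear count alike.

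Four further inferences are tempting and should not be drawn.

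- That harms go unanalysed *because* they are declared absent. Nothing links the ethics line to the analysis plan, and several events are collected despite it.
- That allergy is named as a trial event. It is a baseline exclusion, which is a precaution.
- That families are misinformed. The consent pages were not available for review.
- That the 8.0% limit reveals a flaw in this trial. It follows from arm size alone.

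It can also be said that a harms table would not settle differences between methods. At the power shown, that is right, and it limits the table to description. Finally, the flow chart was not available and may show how exclusions are tracked. Even so, the written criteria would still exclude the event, and the failure list would still omit it.

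**Conclusion.** The point holds in this form. The statement of no harms conflicts with the protocol's own text. More important, one harm arising from the allocated procedure would be dropped uncounted if the plan were followed as written. Extraction is left out in a similar way, and two other events have no stated record. Abscess, fistula, pain and periapical lesions are compared, but not visibly as harms.

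The effect on the success rates cannot be sized without an exposure rate; step 5 gives its direction within an arm. The conclusion rests on three readings: the envelope is opened before excavation begins, the exclusion applies to children already allocated, and no separate safety procedure exists outside the supplied text. The sample size is unaffected.

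**What to change.** 1. Replace the statement in the ethics section with the foreseeable risks the protocol already names, and check that the consent text agrees.
2. For every randomised child, record pulp exposure or bleeding, reactions to materials, anesthesia use, abscess or fistula, and extraction.
3. Tabulate these by randomised arm with counts, percentages and exact confidence intervals, labelled as a descriptive safety summary.
4. Move pulp exposure or bleeding out of the exclusion criteria for allocated children, keep those children in the reported population, and state in advance how they enter the success analysis. Clinical management of such teeth is a separate matter for the investigators.

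The cost is protocol wording, a few form fields and one table, with no extra visits and no change in sample size.

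### The study calendar closes evaluation in month 12 and analyses in month 13, but the 12-month recalls fall due in months 15 and 16

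*Combined protocol and SAP*

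**What the plan says.** The task table under Duration of the study has one header, months 1 to 17, shared by every row, and the section gives "Estimated time: 17 Months". Its rows are ticked as follows:

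- "Patient recruitment": months 2 and 3
- "Treatment procedures": months 3 and 4
- "Clinical and radiographic success of the CMCR": months 4 to 12
- "Time required for caries removal", and likewise pain, microbiology and the quality-of-life questionnaire: month 4 only
- "Data management and statistical analysis": month 13 only
- thesis writing: months 14 to 16
- thesis submission: month 17

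The Follow up section states "All patients will be recalled after 3-, 6- and 12-month intervals". The abstract and the Clinical evaluation section give the same three times, and the Radiographic evaluation section asks for films at 6 and 12 months after the immediate postoperative one. The PICOT question covers a twelve-month period, the sample size uses one-year success proportions (95% against 67%), and Study outcome places the comparison of treatments after follow-up is over.

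**The concern.** The evaluation row and the single analysis month both come before any child can complete 12 months of follow-up. If the team works to the calendar, the only scheduled analysis contains the 3- and 6-month visits but no 12-month outcome. Twelve months is the time point behind both the study question and the sample size, and clinical and radiographic success is the primary aim. No second analysis is ticked: months 14 to 17 hold only writing and submission. The team would have to choose between a final analysis without the main time point and missing its own dates, and the plan does not say which.

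**Working it through.** **Convention.** Month *m* runs from time *m* − 1 to time *m*. Inputs are the ticks in the task table and the recall times in the Follow up section.

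**The plan's own total.** The last tick (submission) is in month 17, so the stated 17 months reproduces from the table.

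**When the recalls fall due.** Treatment in months 3 and 4 spans time 2 to 4.

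| Recall | Due time | Calendar months | Inside the evaluation row (4 to 12)? |
|---|---|---|---|
| 3 months | 2 + 3 = 5 to 4 + 3 = 7 | 6 and 7 | yes |
| 6 months | 2 + 6 = 8 to 4 + 6 = 10 | 9 and 10 | yes |
| 12 months | 2 + 12 = 14 to 4 + 12 = 16 | 15 and 16 | no |

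**Follow-up available.**

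- End of month 12 (evaluation closes): 12 − 4 = 8 to 12 − 2 = 10 months, so 2 to 4 months short.
- End of month 13 (analysis ends): 13 − 4 = 9 to 13 − 2 = 11 months, so 1 to 3 months short.
- The evaluation row ends 16 − 12 = 4 months before the last 12-month visit is due.

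**Does another reading remove the gap?**

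- *All treatment in month 4*, as the time, pain and microbiology ticks might suggest (time 3 to 4): the 12-month recalls fall at time 15 to 16, that is, in month 16. Follow-up is 8 to 9 months at the end of month 12 and 9 to 10 at the end of month 13. The gap remains.
- *Treatment at the earliest conceivable date*, the first day of recruitment (time 1): follow-up at the end of month 12 is 12 − 1 = 11 months, still below 12.
- *Months counted from each child's treatment*: the same header also carries purchasing, recruitment and thesis submission, so it is a project calendar.
- *A table damaged in conversion*: the ticks form a coherent sequence (1; 2–3; 3–4; 4–12; 13; 14–16; 17), and the evaluation row has only nine ticks.

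Figure 1 is not shown. It may give timings, but it could not remove a conflict between this table and the text.

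**Total duration once corrected.** If analysis (1 month), writing (3) and submission (1) keep their present lengths and order after the last visit, the total is 16 + 1 + 3 + 1 = 21 months. If writing overlaps follow-up, and final analysis and submission share one month, it is 16 + 1 = 17. The stated total is therefore not contradicted in itself; the placement of the evaluation and analysis rows is.

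**A smaller mismatch.** Time, pain and microbiology are ticked in month 4 only, although treatment is also ticked in month 3 and these measures belong to the treatment session. For the bacterial counts, Study outcome says "at the treatment visit before and after application of each agent compared to conventional caries removal method". The questionnaire row has the same single tick, although its one-week recall would follow treatment in either month. None of this affects the main result.

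**The case against.** The best case against giving this much weight is that the table is only an estimate that mixes trial tasks with thesis tasks, while the methods text is clear. Every section that names the follow-up asks for 12 months, and Study outcome puts the comparison after follow-up. Someone working from the methods would wait for the 12-month data. The outcome definition, sample size, tests and visits are all untouched. On this view the table holds a slip with little consequence.

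Part of this stands. The intent is clear, and this is a scheduling error rather than a design flaw. But the calendar is where the plan sets the timing of evaluation and analysis, and it places the only analysis before the main time point exists for any child. That goes beyond an editorial slip.

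A second objection is that 21 months is one scenario, since it assumes strict sequence, unchanged task lengths and treatment still in months 3 and 4. That is fair, and the figure should be read only as the sequential case. With treatment as ticked, the firm statement is that complete 12-month data cannot be expected before about the end of month 16.

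**Conclusion.** The concern holds. With treatment in months 3 and 4, no child reaches 12 months before the evaluation row closes (at most 10 months of follow-up) or before the analysis month ends (at most 11). The last 12-month visit is due four months after the row stops. The result rests on the ticks as printed and on recalls counted from the date of treatment. It does not depend on where in months 3 and 4 a child is treated, and even treatment on the first day of recruitment would leave only 11 months when evaluation closes. The error should be corrected before the trial runs to this timetable. It does not alter the sample size or the design.

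**What to change.** - Extend the clinical and radiographic evaluation row to the last child's 12-month visit, about month 16 if treatment ends in month 4.
- Place the final analysis after that visit. Data management can run during follow-up.
- Restate the total duration to match: about 21 months if the later tasks stay in sequence at their present lengths, less if they overlap.
- Align the time, pain and microbiology rows with the treatment row, and set the questionnaire row to follow treatment by one week.
- Bring the calendar into line with the stated follow-up, not the follow-up into line with the calendar, and do not present earlier visits as 12-month results.

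The cost is a corrected table and up to about four more calendar months (21 − 17 = 4), depending on overlap. No patients, visits or procedures are added beyond those already planned.

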APPENDIX I

Table (1): ICDAS severity criteria⁽⁵⁴⁾

Score	Criteria
0	No change in enamel translucency with prolonged air drying
1	First visual change in enamel (after prolonged air drying)
2	Distinct visual change in enamel
3	Localized enamel breakdown or discolored enamel with no visible dentin involvement
4	Underlying dark shadow from dentin
5	Distinct cavity with visible dentin
6	Extensive distinct cavity with visible dentin

APPENDIX III

[figure not shown]

Figure (2): Wong-Baker FACES Pain Rating Scale

[figure not shown]
APPENDIX IV

Table (2): Evaluation scores criteria of atraumatic restorative treatment proposed by Phantumvanit.⁽⁴⁵⁾

Codes	Description
0	Present, in good condition
1	Present, slight marginal defect, no repair needed
2	Present, marginal defects 0.5-1.0 mm, repair needed
3	Present, marginal defects > 1.0 mm, repair needed
4	Not present, restoration partially or completely missing
5	Not present, restoration replaced by other restoration
6	Tooth missing, exfoliated or extracted
7	Present, slight wear, no repair needed
8	Present, wear > 0.5 mm, repair needed

APPENDIX V

Figure (3): showing 5-points Likert scale

APPENDIX VI

Table (3) Arabic validated version of the child perceptions questionnaire(52)
